### 3.4 Dose Reduction Schema

Toxicities will be evaluated using the Common Terminology Criteria of Adverse Events (CTCAE) version 4.0. Patients developing grade 3 or higher toxicity of any kind, which does not meet the definition of DLT, will call for holding HCQ therapy until the toxicity resolves to grade  $\leq 1$ . Any adverse effect attributed as possibly, probably or definitely related solely to HCQ will result in the dose being held until the adverse effect has resolved to  $\leq$  grade 1 or baseline. If the adverse effect resolves, reinstatement of treatment can occur but at a reduced dose as described below (HCQ Dose Reduction Schema). If the adverse effect recurs at the reduced dose, treatment will be held until the adverse effect has resolved to  $\leq$  grade 1 and when resolved treatment can be reinstated at the next lower dose level. No more than 2 dose reductions are allowed during the maintenance cycles.

Toxicities that may be attributable to HCQ include nausea, vomiting, diarrhea, rash, and visual field changes. If any of these adverse events occur at grade  $\leq 2$ , HCQ may be continued and the adverse event managed with supportive care. With particular regard to visual field deficits patients should be cautioned to report any visual symptoms, particularly difficulty seeing entire words or faces, intolerance to glare, decreased night vision, or loss of peripheral vision. These symptoms of peripheral retinal toxicity should prompt drug discontinuation and ophthalmologic evaluation.

Table: Hydroxychloroquine Dose Escalation Schema

Dose level	HCQ
-1a	200 mg qday (9AM)
1	400 mg qday (9AM)
2	400 mg BID (9AM/9PM)
3	600 mg BID (9AM/9PM)

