### Rationale for TACE to treat HCC

The difference in blood supply to the normal liver parenchyma, dual from the portal vein and hepatic artery, compared to the predominantly hepatic arterial blood supply to HCC, as well as metastatic lesions, allows transarterial chemoembolization (TACE) to be performed with low risk of liver failure or other serious complications(4). TACE is performed by administering high doses of chemotherapeutic agents, most commonly doxorubicin with or without cisplatin and mitomycin-C, into the hepatic artery branches supplying the HCC along with embolic material to slow washout of the chemotherapeutic agents and induce ischemia to the tumor(4). Following chemoembolization, transient elevations in liver function tests (LFTs) can be observed from interruption of hepatic arterial supply to normal parenchyma adjacent to the tumors; however, the majority of studies have shown these effects normalize by one week following therapy without permanent effect(5,6).

Typically, HCC arises in the setting of cirrhosis, and thus orthotopic liver transplant (OLT) is often regarded as the only curative option in patients with localized HCC(3,7). However, the majority of patients with HCC will be outside the criteria for liver transplant to treat HCC and will be of unacceptably high risk for local recurrence or metastatic disease following OLT(3,7). In patients with HCC regardless of stage of disease, TACE has been shown to delay HCC progression, improve local tumor control, and allow downstaging (4,8-11). Two randomized trials demonstrated improved survival among Childs A patients compared to best supportive care(4,12).

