**Phase I: Dose Escalation using “3+3” Cohort Expansion Design**

After initiating HCQ, dose limiting toxicity will be defined as events occurring at any time from initiation of HCQ (Week 0) up to Week 12. All patients who receive at least one day of HCQ will be included in the toxicity analysis.

DLT definition:

Toxicities will be graded according to the Common Terminology Criteria of Adverse Events (CTCAE) version 4.0. A DLT will be defined as one or more of the following occurring any time during the defined DLT period from initiation of HCQ (i.e Day -42 to -28) to completion of HCQ therapy 4 weeks following second TACE (Day 56 to Day 63): (1) grade 3 or higher hepatobiliary complication, except hepatic pain; (2) grade 4 or higher hepatic pain; (3) grade 3 or higher abnormality of liver function tests including total bilirubin (i.e. >3x the upper limit of normal) and transaminases (i.e. >5x the upper limit of normal, the Hospital of the University of Pennsylvania defines normal transaminases as AST< 41 IU/L and ALT < 63 IU/L); (4) grade 3 or higher elevation of serum creatinine (i.e >3x baseline or >3x upper limit of normal); (5) grade 3 or higher increase in international normalized ratio (i.e. greater than 2.5x upper limit of normal or >2.5x baseline if anti-coagulated); or (6) any grade 3 or higher toxicity that is possibly or definitely related to treatment. Given the prevalence of baseline thrombocytopenia in patients with HCC, decreases in platelet count will not be evaluated as a DLT.

The initial dose of HCQ will be 400mg PO daily. If the initial dose of HCQ 400mg PO daily incurs DLT, the dose will be reduced to 200mg and an additional 3 patients will be enrolled at this level (see “3+3” Cohort Expansion chart below). If DLTs do not occur at HCQ 400mg PO daily, the dose will be escalated by 400mg increments to a maximally administered dose of HCQ 1200mg (administered as 600mg PO twice daily) with enrollment of each cohort dictated by the “3+3” design (see “3+3” Cohort Expansion and Dose Schema Charts below). The dose may be escalated to the next level once at least 3 patients at a particular HCQ dosage have been observed for 1 month after second TACE (i.e. day 56 to day 63).

“3+3” Cohort Expansion Design Decision Making Regarding Dose Escalation

“3+3” Cohort Expansion Design Decision Making Regarding Dose Escalation	
Number of Patients with DLT at a Given Dose Level	Escalation Decision Rule
0 out of 3	Escalate

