## 4 Subject Selection and Withdrawal

### 4.1 Inclusion Criteria

1. Patient capable giving informed consent
2. Patient diagnosed with hepatocellular carcinoma of the liver by one of the following methods
  - a. Pathologically confirmed HCC by biopsy, OR
  - b. HCC >2 cm with classic radiographic findings of arterial phase enhancement with venous phase washout and pseudocapsule formation on contrast enhanced MRI or CT, OR
  - c. Lesion greater than 2 cm with probable imaging features of HCC and imaging findings of cirrhosis and/or portal hypertension or a serum alphafetoprotein (AFP) greater than 200 ng/mL.
3. Patient not candidate for orthotopic liver transplantation at the Hospital of the University of Pennsylvania based on review of patient imaging and history at multidisciplinary Hepatic Tumor Conference at the Hospital of the University of Pennsylvania
4. Age  $\geq 18$  years old
5. Albumin > 2.4 g/dL; Total bilirubin < 2 mg/dL; INR  $\leq 1.5$ ; Creatinine < 2.0 mg/dL; AST  $\leq 121$  IU/L; ALT  $\leq 189$  IU/L
6. Child-Turcotte-Pugh Classification A or B
7. Eastern Clinical Oncology Group performance status 0 or 1

CONFIDENTIAL

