### 5.5 Subject Compliance Monitoring

Prior to TACE and with each follow-up phone call and clinical visit, the patient will be asked about their compliance with taking HCQ (e.g. patients will be asked if they have missed any doses of HCQ and this information will be recorded). Any reported missed doses will be recorded. Patients who miss greater than 5 consecutive days of therapy will be deemed non-compliant and asked to withdraw from the study. Non-compliant patients will be replaced in the dose escalation phase of the trial.

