### **6.5 Week 6:**

All patients will have laboratory assessments (CBC, PT/INR, CMP) to check for DLT.

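### The hold rule in 3.4 for grade 3 non-DLT toxicity has no return-to-baseline option, and the missed-dose rule in 5.5 does not exempt the holds that 3.4 orders

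*Combined protocol and SAP*

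**What the plan says.** Section 3.4 (Dose Reduction Schema) contains two hold rules.

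- **First rule.** For events of grade 3 or above, "toxicity of any kind, which does not meet the definition of DLT, will call for holding HCQ therapy until the toxicity resolves to grade"; the level required is 1 or lower. No other recovery target is given.
- **Second rule.** Adverse effects attributed solely to HCQ are held until they reach "grade 1 or baseline. If the adverse effect resolves, reinstatement of treatment can occur but at a reduced dose". A recurrence leads to a further step down, with at most two reductions.

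Sections 3.1 and 3.2 take platelet falls out of the DLT definition: "Given the prevalence of baseline thrombocytopenia in patients with HCC, decreases in platelet count will not be evaluated as a DLT". The laboratory entry limits in 4.1 begin "Albumin > 2.4 g/dL; Total bilirubin < 2 mg/dL" and go on to INR, creatinine, AST and ALT. There is no platelet limit.

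Blood counts are scheduled for everyone at Weeks 2 and 6. The Week 6 entry reads "All patients will have laboratory assessments (CBC, PT/INR, CMP) to check for DLT". They are scheduled again at Week 10 for patients not having a second TACE that week.

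Section 5.5 (Subject Compliance Monitoring) states "Patients who miss greater than 5 consecutive days of therapy will be deemed non-compliant and asked to withdraw from the study". It continues: "Non-compliant patients will be replaced in the dose escalation phase of the trial". The withdrawal sentence is not limited to one phase; the replacement sentence is.

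**The concern.** The plan recognises that many of these patients have low platelets at entry and keeps platelet falls out of the DLT count for that reason. The hold rule does not carry that allowance through. For a patient already at grade 2, a return to entry level does not release the hold, although the second rule in the same section would accept it.

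A hold that cannot be released, or is released late, then meets 5.5. Read literally, a patient who stops HCQ because the protocol orders it becomes non-compliant on day 6. The patient is asked to withdraw and, in dose escalation, is replaced. That cuts across the restart that 3.4 plans for.

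In Phase I, the stake is who counts towards the 3+3 decision. In Phase II, a withdrawn patient stays in the intention-to-treat denominator (7.3), and response is assessed at withdrawal (4.4.1), possibly before the Week 12 or 14 imaging.

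**Working it through.** **1. One patient through the rules.** Entry at platelet grade 2 is permitted by 4.1. The Week 2 count shows grade 3. This is not a DLT (3.1, 3.2), so the first hold rule applies. Back at grade 2, the patient is at baseline but not at grade 1 or lower, so the hold continues. Once it has lasted more than 5 consecutive days, 5.5 applies unless ordered holds are exempt, and no sentence in 3.4, 4.4, 5.2 or 5.5 exempts them.

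**2. Can a hold exceed 5 days?** Week 2 to Week 6 is 4 × 7 = 28 days. Week 6 to the check before a second TACE at Week 8 is 2 × 7 = 14 days. A hold that waits for the next scheduled test therefore exceeds 5 days, though an unscheduled test could end it sooner. The only recovery time in the documents is in 1.1, for liver tests after TACE: "the majority of studies have shown these effects normalize by one week following therapy without permanent effect". It is weak support, because grade 3 liver test abnormalities are themselves DLTs, apart from the day after TACE that 3.2 excludes.

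**3. Phase I size.** The documents give no hold rate. Let h be the share of patients with a non-DLT hold over 5 days, assumed at 5%, 10% or 20%.

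- At least one such patient among 6: 1 − (1 − h)^6 = 0.26, 0.47, 0.74.
- Extra patients if all are replaced and all 18 Phase I places are filled: 18h/(1 − h) = 0.95, 2.0, 4.5. The maximum of 58 has no allowance for these.
- Probability that a level passes the 3+3 rule at DLT rate p: (1 − p)^3 + 3p(1 − p)^5. With d the DLT rate in other patients, replacing held patients gives p = d. Keeping them gives p = (1 − h)d + hkd, where k is their relative DLT risk.

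| d | Replaced | Kept, k = 0.5 (h = 5, 10, 20%) | Kept, k = 1 | Kept, k = 2 (h = 5, 10, 20%) |
|---|---|---|---|---|
| 0.10 | 0.906 | 0.910, 0.914, 0.922 | 0.906 | 0.898, 0.889, 0.871 |
| 0.20 | 0.709 | 0.719, 0.730, 0.752 | 0.709 | 0.687, 0.665, 0.622 |

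The largest gap between replacing and keeping is 0.709 − 0.622 = 0.087, and its sign depends on k, which the documents do not give.

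**4. Phase II size.** The plan's own figures come first, with stage 1 of 16 patients as in 7.1.

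- Stopping at 7 or fewer of 16 when the true rate is 40% has probability 0.716, which matches the stated 72%.
- The written rule of 23 or more of 46 gives power 0.829 at 60% and type I error 0.077.
- The stated 0.80 and 0.05 correspond to 24 or more (0.801 and 0.049). That mismatch is a separate matter; both thresholds are shown below.

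Now assume that every held patient is withdrawn and counted as not CR. The response rate becomes 0.60(1 − h).

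| h | Rate | P(stop at stage 1) | Power, ≥23 | Power, ≥24 |
|---|---|---|---|---|
| 0 | 0.60 | 0.142 | 0.829 | 0.801 |
| 5% | 0.57 | 0.206 | 0.736 | 0.690 |
| 10% | 0.54 | 0.283 | 0.617 | 0.554 |
| 20% | 0.48 | 0.466 | 0.341 | 0.271 |

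If held patients stay on study, have their imaging on schedule and respond as the others do, the rate stays at 0.60 and no power is lost.

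**The case against.** The strongest reply is that 5.5 is about compliance. A patient who stops because 3.4 says so is complying, and the opposite reading would defeat the restart and two-reduction path. This stands as the natural reading. It does not remove the case for writing it down, because 5.5 ends in withdrawal and replacement. It also does not touch the missing baseline option.

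A reader might infer that held or reduced patients have no place in the 3+3 decision. The documents do not support that. Section 5.3 assigns each patient to a dose level, 3.1 keeps everyone with one day of HCQ in the toxicity analysis, 3.2 makes DLT and MTD the Phase I primary endpoints, and 7.3 analyses primary endpoints by intention to treat. Together these largely place a kept patient at the assigned level. What stays open is mainly the patient who has been replaced.

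A reader might also infer that DLTs after withdrawal would be lost because 4.4.2 secures only survival data. That is too strong. Section 4.4.2 sets survival as a minimum, and 8.2 requires adverse events to be recorded up to 6 months after the last HCQ dose.

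The class of events is narrow as well. DLT criterion 6 captures grade 3 events possibly or definitely related to treatment, which leaves mainly platelet falls, grade 3 hepatic pain and unrelated events. Section 3.4 does not list platelet falls among toxicities attributable to HCQ. Section 8.1 foresees more frequent testing after an abnormal result, which would shorten some holds. Finally, 18 Phase I places is a maximum: a level with no DLT in 3 escalates after three patients (0.9^3 = 0.73 at a 10% DLT rate), so there is often slack. All of this keeps the expected number of affected patients down.

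**Conclusion.** The concern holds in two specific respects. First, the first hold rule in 3.4 sets a recovery target that a patient with grade 2 platelets at entry can meet only by improving on entry status. Second, 5.5, taken literally, asks patients held by order to withdraw in either phase and replaces them in dose escalation.

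The effect on the MTD is probably small. Over the ranges assumed, replacing versus keeping held patients moves the chance of passing a level by 0 to 9 percentage points, in a direction the documents do not settle.

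The Phase II figures (0.83 falling to 0.74, 0.62 or 0.34 under the written 23-of-46 rule) should not be read as the trial's expected power. They rest on assumed hold rates, on every held patient being withdrawn, and on none counting as CR. They bound the harm of the literal reading; under the natural reading, with imaging as scheduled, there need be no loss. The change is worth making because both rules act on individual patients during the trial and the correction costs almost nothing.

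**What to change.** Make two changes.

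1. In the first hold rule of 3.4, set the recovery target as 'resolves to grade 1 or lower or baseline', in line with the second rule.
2. In 5.5, add: 'Days on which HCQ is held under 3.4 are not missed days; the patient stays on study at the assigned dose level for the 3+3 decision, is followed for DLT to the end of the DLT period and has the scheduled response imaging.'

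The cost is one phrase and one sentence. The DLT definition, the 3+3 table and the sample size do not change. The downside is that a few held or reduced patients will count at a level with less than full exposure to its dose.

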## 4 Subject Selection and Withdrawal

### 4.1 Inclusion Criteria

1. Patient capable giving informed consent
2. Patient diagnosed with hepatocellular carcinoma of the liver by one of the following methods
  - a. Pathologically confirmed HCC by biopsy, OR
  - b. HCC >2 cm with classic radiographic findings of arterial phase enhancement with venous phase washout and pseudocapsule formation on contrast enhanced MRI or CT, OR
  - c. Lesion greater than 2 cm with probable imaging features of HCC and imaging findings of cirrhosis and/or portal hypertension or a serum alphafetoprotein (AFP) greater than 200 ng/mL.
3. Patient not candidate for orthotopic liver transplantation at the Hospital of the University of Pennsylvania based on review of patient imaging and history at multidisciplinary Hepatic Tumor Conference at the Hospital of the University of Pennsylvania
4. Age  $\geq 18$  years old
5. Albumin > 2.4 g/dL; Total bilirubin < 2 mg/dL; INR  $\leq 1.5$ ; Creatinine < 2.0 mg/dL; AST  $\leq 121$  IU/L; ALT  $\leq 189$  IU/L
6. Child-Turcotte-Pugh Classification A or B
7. Eastern Clinical Oncology Group performance status 0 or 1

CONFIDENTIAL

## **4.2 Exclusion Criteria**

1. Prior TACE to the HCC(s) to undergo TACE during this protocol
2. Active GI hemorrhage within 2 weeks of study enrollment
3. Ascites refractory to medical therapy
4. Contraindication to receiving HCQ or TACE
5. Women who are pregnant or nursing
6. Participation in another concurrent treatment protocol

## **4.3 Subject Recruitment and Screening**

This trial is designed to be the initial prospective phase I-II investigation of the safety and effectiveness of combined HCQ and TACE for unresectable HCC. No clinical trials regarding the safety or efficacy of combination of TACE and HCQ have been or are being conducted. Patients will be recruited from the Interventional Oncology Clinic and the multidisciplinary Hepatic Tumor clinic at the Hospital of the University of Pennsylvania. Historically, approximately 50-60 new patients undergo initial TACE at HUP each year as therapy for unresectable HCC. During the initial consultation with Interventional Radiology, patients will be screened and recruited for this trial. Patients who are interested in enrollment will have a full discussion of the risks/benefits of combined therapy and be allowed to address any concerns or questions regarding combined therapy. We expect approximately 5 years will be needed complete enrollment and follow up. The knowledge gained from this phase I-II clinical trial will establish the safety of combined therapy, assess the efficacy in terms of complete response by imaging, and will allow for accurate estimate of the number of patients needed to adequately power larger phase II and III clinical trials.

## **4.4 Early Withdrawal of Subjects**

### **4.4.1 When and How to Withdraw Subjects**

- PI Decision: Subjects may be withdrawn at any time during the study if the PI believes it is in the subject's best interest. In this event, the reasons for withdrawal will be documented.
- Subject Participation: Refusal to continue treatment, follow-up, comply with the protocol or withdrawal of consent. In this event, the reasons for withdrawal will be documented.

Patients withdrawing from the study will be entitled to pursue all treatment options available for the treatment of HCC without prejudice from the providing physicians.

Once the subject has discontinued treatment, the primary reason for discontinuing treatment must be clearly documented in the subject's records and on the CRF. The investigator will assess each subject for response at the time of withdrawal.

### **4.4.2 Data Collection and Follow-up for Withdrawn Subjects**

Even though subjects may be withdrawn prematurely from the study, it is imperative to collect at least survival data on such subjects throughout the protocol defined follow-up period for that subject. Such data is important to the integrity of the final study analysis since early withdrawal could be related to the safety profile of the experimental therapy. If a subject withdraws consent to participate in the study, attempts will be made to obtain permission to record at least survival data up to the protocol-described end of subject follow-up period. Methods that may be used to obtain survival data will include phone calls to the subject, phone calls to next-of-kin if possible, and certified letters to the subject or next-of-kin. If permission to collect or the specific survival data cannot be obtained after 4 phone calls and 4 letters to the subject and/or next-of-kin, the patient will be regarded as lost to follow up.

CONFIDENTIAL

This material is the property of the University of Pennsylvania. Do not disclose or use except as authorized in writing by the study sponsor

## 5 Study Drug

### 5.1 Description

Hydroxychloroquine (HCQ) Sulfate, known by the trade name Plaquenil, is a colorless crystalline solid with the chemical structure 2-[[4-[(7-Chloro-4-quinolyl)amino]pentyl]ethylamino] ethanol sulfate. HCQ sulfate tablets come in 200mg doses, equivalent to 155 mg of the free HCQ base, for oral administration. Inactive Ingredients contained in HCQ Sulfate tablets include: Dibasic Calcium Phosphate, Hydroxypropyl Methylcellulose, Magnesium Stearate, Polyethylene glycol 400, Polysorbate 80, Corn Starch, Titanium Dioxide.

### 5.2 Treatment Regimen

Dose may range from 200-1200mg orally according to cohort, which the patient is assigned as dictated by "3+3" design. The initial dose will be HCQ 400mg PO daily. Therapy will begin prior to TACE for approximately 28 days. The patient will continue HCQ therapy for approximately 8 weeks following initial TACE. Thus, total duration of HCQ therapy will be approximately 12 weeks. Patient medication compliance with HCQ will be assessed and documented at each follow-up phone call and clinical visit (e.g. patients will be asked if they have missed any doses of HCQ and this information will be recorded).

Table: Hydroxychloroquine Dose Escalation Schema

Dose level	HCQ
-1a	200 mg qday (9AM)
1	400 mg qday (9AM)
2	400 mg BID (9AM/9PM)
3	600 mg BID ( 9AM/9PM)

### 5.3 Method for Assigning Subjects to Treatment Groups

Patients will be assigned to a dosage level of HCQ with enrollment according to "3+3" cohort design as described above starting with an initial dosage of HCQ 400mg PO daily. Unblinded dose escalation according to the "3+3" design is desired to allow for close monitoring of patient symptoms/toxicity prior to escalation to the next dose.

### 5.4 Preparation and Administration of Study Drug

Following enrollment, the subject will be prescribed an assigned dose of hydroxychloroquine. Patients will be unblinded to the dose of therapy. Since hydroxychloroquine is an FDA approved drug, the prescription may be filled at a pharmacy, which is most convenient to the patient to facilitate compliance with therapy.

### 5.5 Subject Compliance Monitoring

Prior to TACE and with each follow-up phone call and clinical visit, the patient will be asked about their compliance with taking HCQ (e.g. patients will be asked if they have missed any doses of HCQ and this information will be recorded). Any reported missed doses will be recorded. Patients who miss greater than 5 consecutive days of therapy will be deemed non-compliant and asked to withdraw from the study. Non-compliant patients will be replaced in the dose escalation phase of the trial.

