$\geq 2$	Stop Dose Escalation 
 
• This dose exceeds the MTD
 
• Three additional patients will be entered at the next lowest dose level if only 3 patients were treated previously at that dose
 

1 out of 3	Enter 3 more patients at this dose level 
 
• If 0 of these 3 additional patients experience DLT, proceed with dose
 

CONFIDENTIAL

This material is the property of the University of Pennsylvania. Do not disclose or use except as authorized in writing by the study sponsor

	
escalation to the next level
 
 
• If 1 or more of these 3 additional patients experience DLT, then dose escalation is stopped. This dose level exceeds the MTD
 
• Three additional patients will be entered at the next lowest dose level if only 3 patients were treated previously at that level
 

≤1 out of 6 at the highest tolerable dose	This is considered the MTD. At least 6 patients must be enrolled at the MTD.

Table: Hydroxychloroquine Dose Escalation Schema

Dose level	HCQ
-1a	200 mg qday (9AM)
1	400 mg qday (9AM)
2	400 mg BID (9AM/9PM)
3	600 mg BID (9AM/9PM)

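### Section 5.5 replaces 3+3 patients only for runs of whole missed days, never for the share of assigned doses taken, so an under-dosed patient without a DLT counts as a full observation at the assigned level

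*Combined protocol and SAP*

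**What the plan says.** Section 5.5 (Subject Compliance Monitoring) defines non-compliance once: "Patients who miss greater than 5 consecutive days of therapy will be deemed non-compliant and asked to withdraw from the study". It then links this to the escalation design: "Non-compliant patients will be replaced in the dose escalation phase of the trial". Adherence is self-reported. Under Section 5.2, "patients will be asked if they have missed any doses of HCQ and this information will be recorded", and Section 5.5 adds that "Any reported missed doses will be recorded". Neither section says what the recorded total is used for.

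Section 3.1 (Phase I dose escalation) states that "All patients who receive at least one day of HCQ will be included in the toxicity analysis". It allows escalation "once at least 3 patients at a particular HCQ dosage have been observed for 1 month after second TACE". The decision table counts DLTs only. After 1 DLT in 3, for example, it reads "If 0 of these 3 additional patients experience DLT, proceed with dose" escalation. Levels 2 and 3 are dosed twice daily, at 400 mg and 600 mg per dose.

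Section 3.4 provides for HCQ to be held for certain toxicities and restarted at a reduced dose. It does not say whether held days are missed days under Section 5.5, or at which level such a patient is counted.

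Sections 7.2 and 7.3 define no DLT-evaluable set. The medical monitor's review before escalation (Section 8.6) is for DLT and sets no exposure condition.

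**The concern.** In a 3+3, a patient without a DLT supports a dose level only if the patient received something close to that dose. Section 5.5 is the only rule that removes inadequately exposed patients, and it looks at the longest run of missed days instead of the amount taken. A patient can take far less than assigned without a run of 6 missed days, and one skipped dose of a twice-daily pair does not, read literally, make a missed day.

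The decision at each level rests on 3 to 6 patients, so one misclassified patient matters. The MTD then sets the dose for the Phase II cohort of 46, of whom 40 are newly treated and 6 come from Phase I.

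Section 1.5 gives a reason to take this seriously. In a rheumatoid arthritis study, nausea, vomiting and abdominal pain were dose limiting at 800 and 1200 mg/day, the daily totals of levels 2 and 3. Such symptoms could plausibly lead patients to skip doses. Sections 5.4 and 5.8.4 let patients fill prescriptions at any pharmacy and dispose of unused tablets themselves, and the plan describes no pill count to check self-report.

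**Working it through.** **The plan's own figures.** Phase I: 6 patients × 3 levels = 18. Total: 18 + 46 − 6 = 58. Both reproduce. The plan gives no adherence rate, DLT rate or 3+3 operating characteristics, so the check is of the rule itself.

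**Inputs from the documents.** Flag: more than 5 consecutive missed days (5.5). Duration: about 12 weeks = 84 days (5.2). Levels 1, 2 and 3: 400, 800 and 1200 mg/day (3.1). A level passes on 0/3, or on 1/3 followed by 0/3; the MTD needs at most 1/6 (3.1).

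**Step 1: skipped evening doses.** No whole day is missed, so the patient is never flagged. Level 3: 1200/2 = 600 mg/day, below level 2 (800). Level 2: 800/2 = 400 mg/day, the level 1 total.

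**Step 2: limiting case.** Repeating 5 days missed and 1 taken never gives a run of 6. Days taken: 84/6 = 14, or 17%. This marks the boundary of the rule and is not a prediction.

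**Step 3: scattered missed days.** Assume each day is missed independently with probability q. Track the current run of missed days (0 to 5, with 6 absorbing): each day it grows by one with probability q and resets to 0 with probability 1 − q. After 84 days, the probability of having been flagged is:

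| Share of days missed, q | P(flagged) |
|---|---|
| 0.20 | 0.004 |
| 0.30 | 0.040 |
| 0.40 | 0.180 |
| 0.50 | 0.482 |

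A patient missing half of all days is more likely than not to go unflagged.

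**Step 4: effect on the 3+3.** Let a share f of the counted patients be under-dosed and unflagged, with DLT risk pU, against pF at full dose. The average risk is p = (1 − f)pF + f·pU.

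P(level passes) = (1 − p)³ + 3p(1 − p)² × (1 − p)³ = (1 − p)³ + 3p(1 − p)⁵.

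Example with pF = 0.40 and pU = 0.15:
- f = 0: p = 0.40, so 0.216 + 0.093 = 0.309.
- f = 0.4: p = 0.6 × 0.40 + 0.4 × 0.15 = 0.30, so 0.343 + 0.151 = 0.494.

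The values of pF, pU and f are assumptions:

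| pF, pU | f = 0 | f = 0.2 | f = 0.4 |
|---|---|---|---|
| 0.20, 0.15 | 0.709 | 0.730 | 0.752 |
| 0.30, 0.20 | 0.494 | 0.536 | 0.578 |
| 0.40, 0.30 | 0.309 | 0.343 | 0.378 |
| 0.40, 0.15 | 0.309 | 0.396 | 0.494 |

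For the MTD rule, P(at most 1 of 6) = (1 − p)⁶ + 6p(1 − p)⁵. In the last row this gives 0.233, 0.319 and 0.420.

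The shift is upward in every row, because p falls whenever pU < pF.

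**The case against.** **Size.** DLT items 1 to 5 (hepatobiliary, liver function, creatinine and INR events) carry no attribution test, so events caused by TACE count at any HCQ dose. That narrows the gap between full and partial dosing. Section 1.5 also reports that in all but one of the other HCQ cancer trials no DLT was identified and 1200 mg/day was easily reached. This stands: with 20% against 15%, the shift is only about 4 points at 40% under-dosing. The 18-point shift belongs to the widest gap tabulated.

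**Certainty.** A reader might infer that under-dosed patients are scored DLT-free, or that the MTD is shown to be biased upward. The documents support neither. Section 3.1 includes everyone with at least one day of HCQ, so a DLT in an under-dosed patient counts; and no adherence data are given, so the bias is a risk of the rule.

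**Extreme patterns.** Section 4.4.1 lets the investigator withdraw a patient at any time and lists refusal to comply with the protocol, and adherence is asked about repeatedly. A patient reporting 14 of 84 days need not be kept. This mitigates, but 4.4.1 sets no threshold and no replacement rule, and it does little about skipped evening doses.

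**Reverse misclassification.** A reader might add that a patient with a single 6-day gap, who could have taken 78 of 84 days (93%), is lost needlessly and would be saved by a dose-share rule. That gain is largely illusory: Section 5.5 still asks this patient to withdraw.

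**A simple cut-off could do harm.** Replacing every DLT-free patient below a dose share would remove patients whose HCQ was held or reduced for toxicity under Section 3.4. They fell short because of toxicity; replacing them discards that evidence and could itself push the MTD up. This objection stands, and the fix must separate the two groups.

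**Conclusion.** The gap is real. The run-of-days rule is the only exposure criterion governing replacement in the 3+3, and nothing in Sections 3.1, 4.4.1, 7.2, 7.3 or 8.6 adds a total-dose condition. A DLT-free patient who took half of a twice-daily dose, or who missed many scattered days, counts in full at the assigned level.

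The direction is toward too high an MTD, provided that DLT risk does not fall as dose rises. The size cannot be fixed from the documents: at 40% under-dosing the change in the chance of passing a level runs from 0.04 to 0.19 across the assumed pairs. The flag rates also assume independent missed days; clustered misses would be flagged more often.

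A reader might conclude that levels 2 and 3 are singled out as untested in this combination. The documents do not support that: Sections 1.4 and 4.3 report no trial of HCQ with TACE at any dose. What distinguishes these levels here is twice-daily dosing, which makes half-dosing invisible to the rule.

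**What to change.** Add to Sections 3.1 and 5.5 a definition of the DLT-evaluable patient for the 3+3 count:

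- A patient without a DLT counts only after taking at least a pre-set share of the doses assigned over the DLT period, counted in doses and not days. The sponsor should choose the share; 80% is an example.
- Patients below the share through missed doses unrelated to toxicity are not evaluable and are replaced.
- Any patient with a DLT counts, whatever the dose taken.
- Patients below the share because of toxicity-related holds or reductions under Section 3.4 are not replaced as merely non-evaluable. Sections 3.1, 3.4 and 5.5 must be reconciled to state how these patients count and at which level.
- Percent of assigned dose taken is tabulated by dose level alongside the DLT table in Section 7.2.

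This alters counting only. It changes no dosing, hold or withdrawal instruction.

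The cost is a short amendment and one variable derived from missed doses already recorded. Phase I may need a few more patients, and its 18 carries no stated allowance for replacements: at assumed non-evaluable rates of 10% and 20%, 18/0.9 = 20 and 18/0.8 = 22.5, so 23. The measure would still rest on self-report.
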